5.3.3 Visit 13 (Month 15/Wk 65 [ $\pm 2$ wk]), Visit 14 (Month 18/Wk 78 [ $\pm 2$ wk]), Visit 15 (Month 21/Wk 91 [ $\pm 2$ wk]), Visit 16 (Month 24/Wk 104 [ $\pm 4$ wk])

During the first year of LT-OLE, the following assessments will be conducted every three months on day 4 (-1) post-dose for all patients:

- Auxology measurements: Actual height (average of three consecutive measurements) measured on a calibrated wall mounted stadiometer.
- Overall health status assessment, including complete physical examination and vital signs assessment.
- Individual dose adjustment based on weight.
- AEs, local tolerability, and concomitant medications.

Effective Date: Date of final electronic approval

- Urine pregnancy test at every visit once a female patient reports first menstrual cycle (menarche).
- Assessment of biochemical markers: IGF-1, IGF-1 SDS, IGFBP-3 and IGFBP-3 SDS serum levels.
- Assessment of MOD-4023 serum levels.
- Assessment of anti-MOD-4023 Ab.
- Fundoscopy (if there are signs or symptoms indicative of benign intracranial hypertension).
- Return of used and unused injection devices to the site and diary card.
- Drug dispensing and accountability.

The following assessments will also be conducted at Visit 13 (Month 15), Visit 14 (Month 18) and Visit 16 (Month 24) on day 4 (-1) post-dose visits:

- Safety laboratory tests: chemistry, hematology and urinalysis.
- Assessment of thyroid function: TSH, FT4.
- Parameters of glucose metabolism: overnight fasting glucose, overnight fasting insulin, HbA1c.
- Parameters of lipid metabolism: overnight fasting cholesterol, triglycerides, HDL, LDL, Lp(a), FFA.

The following assessments will also be conducted at Visit 16 (Month 24) on day 4(-1) post-dose:

- ECG.
- Bone age.
- Pubertal status.
- For males that are 13 years and older: LH, FSH and testosterone. For females that are 12 years and older: LH, FSH and estradiol.

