### 5.8.9 Laboratory Assessments

All routine clinical laboratory assessments will be performed by central laboratory as provided in [Appendix K](#) according to the schedule in [Appendix A](#), other than urine pregnancy testing, when required, which will be conducted at the local laboratory. The laboratory evaluations will include:

1. Hematology: Red Blood Cell (RBC) count, hemoglobin (HGB), hematocrit (HCT), Mean Cell Hemoglobin (MCH), Mean Cell Hemoglobin Concentration (MCHC), Mean Corpuscular Volume (MCV), White Blood Cell (WBC) count and differential, platelet count, prothrombin time (PT)/international normalized ratio (INR), partial thromboplastin time (PTT) (if indicated only).
2. Serum chemistry: total protein, albumin, total bilirubin, alanine aminotransaminase (ALT), aspartate transaminase (AST), gamma-glutamyl transferase (GGT), lactate dehydrogenase (LDH), creatinine phosphokinase (CPK), alkaline phosphatase, sodium, potassium, calcium, phosphate, blood urea nitrogen (BUN), liver function test (LFT), creatinine.
3. Lipid metabolism: overnight fasting cholesterol, triglycerides, high density lipoprotein (HDL), low density lipoprotein (LDL), lipoprotein a (Lp(a)), Free Fatty Acids (FFA).
4. Glucose metabolism: overnight fasting glucose and insulin, HbA1C.
5. Thyroid function: TSH, FT4.
6. Immunogenicity: anti-MOD-4023 Ab (MOD-4023 arm only during the main study and all patients during the LT-OLE) and Abs to r-hGH (all patients). It is recommended that if the Genotropin patients normally administer their drug in the morning, that they wait on those visit days to administer the Genotropin® until after the blood sampling.
7. IGF-1, IGF-1 SDS, IGFBP-3 and IGFBP-3 SDS levels.
8. MOD-4023 serum levels (MOD-4023 arm only during the main study and all patients during the LT-OLE).
9. Urinalysis: pH, glucose, ketones, erythrocytes, leukocytes, protein.
10. Urine pregnancy test.
11. Luteinizing hormone (LH), Follicle-stimulating hormone (FSH) and testosterone (for males that are 13 years and older).
12. LH, FSH and estradiol (for females that are 12 years and older).

For further details on blood sample collection and shipment to the central laboratory, please refer to the Central Laboratory Manual.

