SHOX gene evaluation aa	X												
IGF-1, IGF-1 SDS, IGFBP-3, and IGFBP-3 SDS	X		X		X	X	X			X	X		
MOD-4023 serum levels bb			X	X	X	X		X		X		X	
Thyroid function (TSH, fT4)	X		X			X	X			X	X		
Glucose metabolism cc	X		X			X	X			X	X		
Lipid profile dd			X			X	X			X	X		
LH, FSH and testosterone ee											X		
LH, FSH and estradiol ff											X		

x Urinalysis: pH, glucose, ketones, erythrocytes, leukocytes, protein.

y Two (2) different GH stimulation (provocation) tests (ITT, with serum cortisol response to hypoglycemia if insulin stimulation test is chosen OR arginine test/clonidine test/glucagon test (with or without propranolol)/L-dopa plus propranolol.

z ACTH or CRH stimulation test will be conducted if morning cortisol is below 190 nmol/L (7 µg/dL), and only if the patient was not previously assessed for the hypothalamus-pituitary-adrenal axis. ITT with serum cortisol response to hypoglycemia is adequate for assessment of adrenal insufficiency and no ACTH stimulation test is required if such results are available. Historical ACTH test is acceptable

aa Historical data is acceptable.

bb For MOD-4023 arm only.

cc Glucose metabolism: fasting glucose and fasting insulin; HbA1c.

dd Lipid profile: overnight fasting total cholesterol, LDL cholesterol and triglycerides, HDL and FFA; Lp(a) once every 3 months.

ee For male patients that are at the age of 13 years and above.

Effective Date: Date of final electronic approval

Study Procedure	Screening		Baseline	Treatment								Follow-up b	
Study Day ( $\pm$ in dy/s)	a -56 to -1		1/	10 (+4)							EOS b		
Study Wk ( $\pm$ in wk/s)	-8 to -1 (+4) a		0 (+4 from Eligibility)		4 (+1)	13 ( $\pm$ 1)	26 ( $\pm$ 1)	26 ( $\pm$ 3)	26 ( $\pm$ 3)	39 ( $\pm$ 1)	52 ( $\pm$ 1)	52 ( $\pm$ 1)	56 ( $\pm$ 5 days)
Study Month	-2		0	0.5	1	3	6	6	6	9	12	12	13
Study Visit	1		2	3	4	5	6	6a c	6b	7	8/10 d	8a c /10 d	9
Abs to r-hGH (Genotropin arm)			X		X	X	X			X	X		
Abs to r-hGH (all patients)	X												
Abs to MOD-4023			X	X	X	X		X		X		X	

ff For female patients that are at the age of 12 years and above.

Effective Date: Date of final electronic approval

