3.5.4. Antibodies

Blood samples for anti-drug antibodies (ADA) will be collected according to the Schedule of Activities in the protocol, including the ADA status (positive, negative, not done or not available) for the following items:

- Anti-human GH (hGH) antibodies
 - neutralizing
 - non-neutralizing
- Anti-somatrogan antibodies
 - neutralizing
 - non-neutralizing

ADA titer will be classified as 0 (i.e., ADA negative), 10, 50, 250, 1250, 6250. Titer values >6250 are reported as 6250.

ADA positivity will be defined as:

- Tested positive after the receipt of drug during the study (either in main period or OLE), if main period baseline was tested negative or titer as 0;
- Post-baseline titer > 4x main period baseline titer, if main period baseline was tested positive.

Otherwise, it will be classified as ADA negative.

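### SAP 3.5.4 does not limit ADA negative to tested children, while the LT-OLE schedule has no anti-hGH sample and children switching from Genotropin have no main-period anti-somatrogon baseline

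*SAP*

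**What the plan says.** SAP 3.5.4 (Antibodies) has samples collected on the protocol's schedule, "including the ADA status (positive, negative, not done or not available) for the following items". The items are "Anti-human GH (hGH) antibodies" and anti-somatrogon antibodies, each split into neutralizing and non-neutralizing.

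The section then defines positivity in two branches:
- With a negative (or zero-titer) main-period baseline, the condition is "Tested positive after the receipt of drug during the study (either in main period or OLE").
- With a positive main-period baseline, the post-baseline titer must exceed four times the baseline titer.

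The definition closes with "Otherwise, it will be classified as ADA negative".

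On sampling, the protocol says:
- **Main study, Appendix A.** The row "Abs to r-hGH (all patients") is marked at screening only. The row "Abs to r-hGH (Genotropin arm") is marked at Visits 2, 4, 5, 6, 7 and 8.
- **LT-OLE, Sections 5.3 and 5.4 and the LT-OLE tables of Appendix A.** The only antibody item is anti-MOD-4023, for example "Assessment of anti-MOD-4023 Ab".
- **Section 5.8.9.** The laboratory list reads "Immunogenicity: anti-MOD-4023 Ab (MOD-4023 arm only during the main study and all patients during the LT-OLE) and Abs to r-hGH (all patients"), while referring to Appendix A for timing.

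On reporting, SAP 6.2.1 commits to the frequency of anti-somatrogon antibodies, if enough data are collected. SAP 6.1.1 allows efficacy summaries by ADA status, positive or negative, without naming the antibody. SAP Appendix 2.1 sets separate annual windows for ADA characterization: one for the main period and one for each OLE year.

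**The concern.** A status of negative should mean that the child was tested and was not positive. Here the rule sends to negative every child who meets neither positivity condition, and two groups can fail to meet them for reasons unrelated to an immune response. One group has no anti-hGH test. The other has no baseline against which an anti-somatrogon result can be judged.

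If the rule is programmed as written, anti-hGH status by randomised arm would partly describe who was sampled. The switcher problem reaches further, because it touches the anti-somatrogon frequency that SAP 6.2.1 commits to report. Either status could also enter the efficacy summaries by ADA status in SAP 6.1.1, since that section does not say which antibody it means.

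**Working it through.** The documents give no anti-hGH rate, so there is no figure to reproduce. The check is a count of scheduled samples followed by a trace of the rule.

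**1. Scheduled post-baseline anti-hGH samples per child (Appendix A)**

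| Randomised to | Main study | LT-OLE |
|---|---|---|
| Somatrogon | 0 | 0 |
| Genotropin | 5 (Visits 4, 5, 6, 7, 8) | 0 |

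Both arms are tested at screening, where a positive result excludes the child (exclusion criterion 6). Visit 2 is the Genotropin arm's pre-dose sample and is not counted.

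**2. The rule applied to a child randomised to somatrogon, anti-hGH**
- The baseline is negative, from screening, so the first branch applies.
- That branch needs a positive test after drug. No test is scheduled, so the condition is not met.
- The default then gives ADA negative. The collected status in the same section would be not done.

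**3. The rule applied to a switcher, anti-somatrogon**
- Section 5.8.9 restricts anti-MOD-4023 testing in the main study to the MOD-4023 arm, and Section 5.2.1 makes the Visit 2 antibody depend on arm. Section 5.2.5 first schedules anti-MOD-4023 in the Genotropin arm at Visit 8, the end of the main period.
- A switcher therefore has no scheduled anti-MOD-4023 result at the main-period baseline.
- Both branches are conditional on a main-period baseline result, so neither applies.
- A positive result at any of the six scheduled OLE Year 1 samples (Visits 11 to 16) then falls through to ADA negative.

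**4. The rule applied to a switcher, anti-hGH**
- A positive at Visits 4 to 8, on Genotropin, satisfies the first branch because main-period results count.
- An overall OLE status would be positive with no OLE test behind it. Under the Appendix 2.1 windows the same result belongs to the main period. The SAP does not say which governs.

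**5. What the literal default could show in the somatrogon arm**

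Assume no anti-hGH result from any other source and N children in the OLE. N is not given, so I take 90 to 110, where 110 is the number planned per arm. The literal default gives 0/N. The exact two-sided 95% upper limit for 0/N is 1 − 0.025^(1/N):
- N = 90: 1 − 0.025^(1/90) = 4.0%
- N = 100: 1 − 0.025^(1/100) = 3.6%
- N = 110: 1 − 0.025^(1/110) = 3.3%

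The correct statement would be 0 tested, rate not estimable.

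Partial testing does not cure the default. If, purely for illustration, 20 of 110 children had a result and 5 were positive, the default gives 5/110 = 4.5%, against 5/20 = 25% of those tested.

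**The case against.** The strongest reply is that the default is being read too literally. SAP 3.5.4 names not done and not available as statuses. The positivity branches speak of test results and titers, so the closing sentence can be taken to cover tested children only. That is a reasonable reading, and it makes the text ambiguous rather than plainly wrong. It does not settle the matter. The four levels describe what is collected, the derived classification has two outcomes, and SAP 6.1.1 uses only positive and negative. Nor does it help the switcher, who is tested and still meets neither branch.

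A reader might also infer that the OLE report will show a 0% anti-hGH rate in the somatrogon arm. The documents do not support that:
- SAP 6.2.1 commits only to anti-somatrogon frequencies, and the SAP's table list is redacted.
- Protocol Section 8.6.8 mentions a summary of both antibodies but gives no period.
- The LT-OLE endpoint includes characterization of the antibody, which may yield hGH-specificity results from anti-MOD-4023 samples. The documents do not say. A missing schedule row therefore does not prove that no assay is run.

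It would also go too far to say that Genotropin-year positives carry into every OLE year, because the Appendix 2.1 windows keep them in the main period for the annual characterization. Nor do the documents rank hGH-binding antibodies as the more important for safety. The LT-OLE endpoint they name is anti-MOD-4023.

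**Conclusion.** The point holds as a defect in a classification rule, not as a prediction of a reported result. It is established that SAP 3.5.4 includes anti-hGH, that the LT-OLE schedule has no anti-hGH sample, that scheduled post-baseline samples are 0 against 5 per child in the main study, and that the default is not limited to tested children. It is also established that both positivity branches need a main-period baseline, which switchers are not scheduled to have for anti-MOD-4023.

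A misleading anti-hGH rate in the somatrogon arm would need three further things: the default overriding the not-done level, no anti-hGH results from characterization or unscheduled tests, and an anti-hGH table. None is stated. The 3.3% to 4.0% upper limits rest on those conditions and on the assumed N.

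Severity is modest. SAP 5.1 plans no hypothesis test in the OLE, and no decision rule depends on ADA status. It is still worth correcting because the rule, followed as written, can give wrong statuses, including for the anti-somatrogon frequency the SAP intends to report.

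**What to change.** Change the SAP wording as follows:

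1. **Negative status (3.5.4).** Class a child as ADA negative for an antibody only with at least one valid post-baseline result for that antibody in the period and no result meeting the positivity rule. Keep all other children who are not positive as not done or not available, outside the denominator.
2. **Baseline and period.** Count only results after the first somatrogon dose toward somatrogon ADA status. For switchers, use the last pre-somatrogon sample as baseline. Section 5.2.5 already schedules one at Visit 8, and Section 5.3 already treats the repeat sample after a gap of more than 90 days as their baseline. State how any overall status relates to the Appendix 2.1 windows.
3. **Source of anti-hGH results.** Say where they come from in the OLE, for example characterization of anti-MOD-4023-positive samples, or delete anti-hGH from OLE ADA status. If characterization is the source, also say how a child with only anti-MOD-4023-negative samples is counted for anti-hGH.
4. **Subgroups (6.1.1).** Name the antibody that defines ADA status.

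In the protocol, reconcile the all-patients wording of Section 5.8.9 with the anti-hGH rows of Appendix A.

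The cost is wording. An assay cost arises only if the sponsor chooses to run anti-hGH on LT-OLE samples and does not already do so. That blood is already drawn for anti-MOD-4023.

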4. ANALYSIS SETS (POPULATIONS FOR ANALYSIS)

Data for all participants will be assessed to determine if participants meet the criteria for inclusion in each analysis population prior to releasing the database and classifications will be documented per standard operating procedures.

The term “full analysis subset” is used to describe the analysis set which is as complete as possible and as close as possible to the intention-to-treat ideal of including all enrolled patients entered the OLE period. The full analysis set will comprise all treated patients who have received at least one dose of active treatment during the main and OLE phase and who provide any follow-up data. The patients will be grouped by their original randomized treatment in the main period.

The analysis populations for reporting are defined in the following table.

Population	Description
Enrolled	All participants who sign the informed consent document and continued in the OLE period.
Evaluable or Full Analysis Set (FAS)	All participants who continue to the OLE period of the study and take at least one complete dose of somatrogan (or partial dose if adverse events prevent completing dose). Participants will be analyzed overall and according to the randomized study drug that originally received in the main period.
Safety Analysis Set	All participants who continue to the OLE period of the study and take at least 1 complete dose of somatrogan (or partial dose if adverse events prevent completing dose). Participants will be analyzed overall and according to the randomized study drug that originally received in the main period.
Per Protocol Set (PP)	Not applicable.

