#### 8.2.1 Safety Analysis Set

The safety analysis set will include all patients who have received at least one dose of study treatment. Patients will be analyzed according to actual treatment received.

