2.1.1. Estimand(s)

The estimand of this study uses the treatment policy strategy and estimates the effect for all participants treated regardless of whether an intercurrent event occurs. Each of them includes the following four attributes:

- Population: All patients who entered OLE period and had at least one dose of somatropin;
- Variable:
 - Annualized height velocity (AHV) at each 12-month interval (cm/year)
 - Height standard deviation score (SDS) and change in height SDS;
 - Change in bone maturation (BM);
 - IGF-1 and IGF-1 SDS levels on day 4 (-1) after somatropin dosing across study visits;
 - IGFBP-3 levels and IGFBP-3 SDS on day 4 (-1) after somatropin dosing across study visits;
 - Pubertal status (according to Tanner stages);
 - For males that are 13 years and older: luteinizing hormone (LH), follicle-stimulating hormone (FSH) and testosterone;

- For females that are 12 years and older: LH, FSH and estradiol
- Intercurrent event: All data after an intercurrent event (discontinuation of treatment, discontinuation of study, etc.), if collected, will be included;
- Population-level summary: descriptive summary for absolute values at each visit and/or change from previous interval.

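### The complete-dose rule in SAP Section 4 can leave an exposed child out of the OLE safety set and FAS, and the narrative beside it defines a different FAS

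*SAP*

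**What the plan says.** SAP Section 4 describes the full analysis set twice.

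- **Narrative.** "The full analysis set will comprise all treated patients who have received at least one dose of active treatment during the main and OLE phase". A second condition in the same sentence is that some follow-up data exist for the child. This largely repeats the LT-OLE definition in Protocol 8.2.5.
- **Table.** It is introduced by "The analysis populations for reporting are defined in the following table". Its FAS row covers participants who continue into the OLE and "take at least one complete dose of somatrogan (or partial dose if adverse events prevent completing dose". Follow-up data are not required. The safety row has the same rule: "take at least 1 complete dose of somatrogan (or partial dose if adverse events prevent completing dose".

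Three other places set a dose or onset condition without asking whether a dose was complete:

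- SAP 2.1.1 (estimand): "Population: All patients who entered OLE period and had at least one dose of" the weekly product.
- SAP 3.5.1: an adverse event is treatment-emergent if it starts on or after the first somatrogon dose in the OLE.
- Protocol 8.2.1: "The safety analysis set will include all patients who have received at least one dose of study treatment". Protocol 8.2.5 is worded similarly on dose and adds the follow-up condition.

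SAP 6.1.1 and 6.2.1 use the FAS for efficacy and antibodies. SAP 6.5 and 6.5.1 use the safety set for the safety tables, and 6.5.1 also lists all adverse events.

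**The concern.** A safety set normally holds everyone exposed. Here the table adds a completeness condition, with an exception that depends on why the dose was incomplete. A child who received part of a dose and stopped for a reason not recorded as an adverse event is exposed, belongs to the estimand population, and can have a treatment-emergent event under 3.5.1. The table nevertheless puts that child outside the set on which treatment-emergent events are tabulated.

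Such doses are foreseeable. Protocol 6.3 allows one prescribed dose to be split into two injections or across two pens, and a child could stop after the first. Children switched from Genotropin meet a new product and device at OLE entry (Protocol 5.3).

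Separately, one section gives the name full analysis set to two different groups. Participants have to be classified before the database is released, so whoever programs the population flags should have a single rule.

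**Working it through.** The plan gives no figure on this point, so the check compares set membership.

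**Step 1. Conventions.** Each child is classified by the most complete somatrogon dose ever taken, and by whether any follow-up data exist. Two readings are assumed. Where a definition says only dose, any amount counts, because neither document defines the term. The narrative is taken to require a dose in the OLE.

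**Step 2. Membership.**

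| Most complete dose | Follow-up data | SAP narrative FAS | SAP table FAS and safety set | SAP estimand population | Protocol 8.2.5 FAS | Protocol 8.2.1 safety set |
|---|---|---|---|---|---|---|
| Complete | Yes | In | In | In | In | In |
| Complete | No | Out | In | In | Out | In |
| Partial, AE | Yes | In | In | In | In | In |
| Partial, AE | No | Out | In | In | Out | In |
| Partial, not AE | Yes | In | **Out** | In | In | In |
| Partial, not AE | No | Out | **Out** | In | Out | In |

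The two SAP versions of the FAS disagree in 3 of the 6 rows. In two rows the narrative is narrower, because of follow-up; in one the table is narrower, because of completeness. The table disagrees with the estimand population and with the Protocol 8.2.1 safety set in the last two rows.

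**Step 3. Who can fall in the last two rows.** The table does not say that the complete dose must be taken in the OLE. If main-study doses count, a child randomised to somatrogon who completed the main study with adequate compliance (LT-OLE inclusion criterion 11) already satisfies the rule. That leaves children switched from Genotropin who never complete a dose. If only OLE doses count, either group could contribute.

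**Step 4. What happens to an event.** An event after that child's partial dose is treatment-emergent under SAP 3.5.1. It appears in the listing of all events under 6.5.1. It is in no treatment-emergent table, because those use the safety set.

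**Step 5. Size.** The documents give no rate of incomplete dosing, so this step is an assumption.

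- Planned entrants, if the 10% dropout allowance holds and every completer continues: 220 × 0.90 = 198 overall and 110 × 0.90 = 99 switched children.
- One excluded child with the only report of a given term: 1/99 = 1.0% becomes 0/98 = 0% in the switched group; 1/198 = 0.5% becomes 0% overall.
- A generous range of 0 to 4 excluded children, with 200 entrants and a 40% event rate: 80/200 = 40.0% if none is excluded. If four are excluded, 80/196 = 40.8% when none had the event and 76/196 = 38.8% when all did.

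**The case against.** The strongest reply is that the SAP states which definition governs. The table is for reporting, and the narrative is largely carried over from the protocol. That stands: it settles which FAS would be programmed. It does not remove the contradictory sentence or the mismatch between the table and 2.1.1.

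The SAP also reserves the right to modify the protocol's plans (Section 2). Protocol 8.2.1 precedes the LT-OLE heading, and the protocol never says whether an incomplete dose counts as a dose. So this is an unexplained departure from the protocol's plain wording, not a prohibited one. The conflict with the SAP's own 2.1.1 and 3.5.1 remains.

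The excluded child is also rare. He or she must never complete a dose, switched children are trained and take the first dose at the site, and the AE exception keeps the main tolerability cases. Pain scored 4 or more is only one route to an adverse event under Protocol 5.8.2; investigator judgement is another. All of this stands and limits the size.

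A reader might infer more than the documents support:

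- *Two competing denominators for treatment-emergent events.* The SAP defines its safety set once; only the FAS has two versions.
- *Growth results depend on the choice.* Growth is summarised as observed with N, mean and SD (SAP 5.2.1, 5.3, 6.1.1). A child without follow-up adds nothing to OLE growth summaries under either definition.
- *Pen information is lost.* Device complaints are reported irrespective of analysis set (Protocol 7.9), and the pen-usability endpoints belong to the main study.
- *A sizeable share of early stoppers disappears.* SAP 6.4.2 names no analysis set for disposition, the Enrolled population has no dose condition, and no rate of early stopping is given.

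**Conclusion.** The point holds as a minor inconsistency with one substantive consequence: the table's rule can drop an exposed child from the FAS, the safety set and every treatment-emergent event table, while the estimand population and the treatment-emergent rule both include that child. The second FAS definition is leftover wording, but it describes a different group under the same name.

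Few children would be affected, possibly none. Overall percentages would move by about a point at most, even with four children excluded in the example above. The more visible effect would be a rare event that is listed but missing from the tables. Growth means would barely change, and no decision is at risk because SAP 5.1 plans no hypothesis test. The conclusion assumes that an unqualified dose means any amount. The table's addition of the word complete suggests that, but neither document states it.

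**What to change.** In SAP Section 4:

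- Define the safety set as all participants who receive any amount of somatrogon in the OLE, whatever the reason a dose was incomplete.
- Define the FAS the same way, so that it matches 2.1.1.
- Delete the complete-dose condition from both table rows, and delete the conflicting narrative sentence.

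Naming the OLE explicitly also settles whether main-study doses count. The planned N at each visit already shows how many children contribute data, so no separate follow-up condition is needed.

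The cost is SAP wording and the two population flags, with no new data and no new analyses. The change should be made before participants are classified for database release.
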